### 7.4 Efficacy

#### Parasitology

- **Asexual parasite counts**

Microscope blood slides will be prepared prior to the first dose of DHA-PQP at screening on Day 1 to confirm the diagnosis of *P. vivax* malaria, and then twice a day, 6-12 hours apart for the first 3 days, or until 2 consecutive negative thick blood smears are obtained. Where the subject receives DHA/PQP < 6 hours from midnight on Day 1, a second Day 1 slide may be omitted.

Microscope blood slides will be prepared at subsequent visits on Days 7, 14, 21, 28, 60, 90, 120, 150 and 180 (refer to Section 7.1 Time and Events table). In addition, blood films should be obtained whenever parasitological re-assessment is required and at the relapse visit or withdrawal visit as applicable. For detailed instructions on the methodology for staining and counting please refer to the SRM.

Slides are considered negative after review of 100 high-power fields. A negative slide refers to the absence of asexual parasites only.

- **Gametocyte counts**

In the same way, thick film slides will be read for gametocytes on Day 1 (prior to the first dose of DHA-PQP) and then twice a day 6-12 hours apart for the first 3 days or until 2 consecutive negative thick blood smears are obtained. Slides will be prepared at subsequent visits on Days 7, 14, 21, 28, 90, 120, 150 and 180 (refer to Section 7.1 Time and Events Table).

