
¹ For the twice daily blood smears on days 1-3, when determining exclusion from the PP population, participants were excluded if they didn't have at least one assessment on each day, without having first demonstrated clearance. The time of the assessments will not be used since visit windows around the 6-12 hour duration have not been defined.
 
² On study days 1-3, participants were scheduled to have twice daily blood smears until they had two consecutive negative smears, 6-12 hours apart. Due to errors in the parasite counts, 3 participants (participant numbers P_n PP and PP) were incorrectly concluded to have negative smears which were in-fact positive, and hence missed a subsequent parasitology assessment during days 1-3. These participants will not be excluded from the PP population as a result of this missed assessment.
	

During the study, the data is reviewed on an ongoing basis, with protocol deviations (PDs) identified by programmatic checks and manual review. These deviations are

assessed by data management and clinical (with input from others as required), and are entered into the deviations log, with the 'Important' flag set accordingly.

The per protocol population exclusion flag is a derived variable in the analysis and reporting dataset (ADaM.ADDV). This variable is not captured in the SI or SDTM datasets. As for the 'important PD' flag, data is reviewed throughout the study to identify participants who should be excluded from the PP population. At DBR, additional programmatic checks are performed by the clinical programming team to further check for PDs. A spreadsheet of any PDs identified is provided to data management and clinical, who will add them to the deviations log with appropriate flags if not already included.

A listing will be produced for the safety population showing the individual participant numbers for each important protocol deviation. A table will be produced showing the number and percentage of participants with major protocol deviations, overall and by type of deviation.

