11.6.3. Efficacy**Efficacy endpoints****Relapse free efficacy at six months**

Relapse is defined as any recurrence of *P. vivax* malaria after clearance of the initial infection.

Participants will be considered to have demonstrated relapse-free efficacy at six months if all of the following are true (also described in [Figure 1](#)):

Participant had a non-zero *P. vivax* asexual parasite count at baseline. Participants who do not meet this criterion will be censored, with time to relapse censored at 0 days.

Participant demonstrated initial clearance of *P. vivax* parasitemia. This is defined as two negative asexual *P. vivax* parasite counts, with at least 6 hours between the counts, and no positive counts in the interval. Participants who do not meet this criterion will be censored with time to relapse censored at 0 days.

Participant has no positive asexual *P. vivax* parasite count at any assessment prior to or on Day 180 visit following initial parasite clearance. Participants who do have a positive count will be considered to have relapsed with time to relapse = (date of first positive count) – (date of Study Day 1) days.

Participants did not take a concomitant medication with anti-malarial activity (excluding study treatment) at any point between Study Day 1 and their last parasite assessment. Participants who did take a drug with anti-malarial activity but never had a positive asexual *P. vivax* parasite count after initial clearance will be censored with time to relapse censored at (date of last negative parasite assessment prior to concomitant medication start) – (date of Study Day 1) days. If a participant has not had a negative assessment prior to the concomitant medication start date, they will be censored at 0 days.

[figure not shown]
Efficacy endpoints

Participant is parasite-free at 6 months. This is defined as a negative asexual *P. vivax* parasite count at the first parasite assessment performed on or after Study Day 170.

Participants who do not have a Day 180 visit and have not already failed or been censored will be censored at (date of final parasite assessment) – (date of Study Day 1) days).

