
A participant will be considered to have had a recrudescence if the following are true:
 
Included in mITT population
 
Participant had a positive P. vivax asexual parasite count at baseline and demonstrates clearance (i.e. two negative asexual P. vivax parasite counts, with at least 6 hours between the counts, and no positive counts in the interval).
 
Participant has a positive genetically homologous asexual P. vivax parasite count on or before Study Day 14, after their zero count in days 1 to 5.
 
The following participants will have a censored time to recrudescence of 0 days:
 
Participant had no asexual P. vivax parasites at baseline.
 
Participant had a positive P. vivax asexual parasite count at baseline but had no subsequent zero asexual parasite count within study Days 1-5.
 
If a participant does not meet the definition of recrudescence, but took a concomitant medication with anti-malarial activity between Study Day 1 and Study Day 14, they will be censored, with time to recrudescence censored at (date of last negative parasite assessment prior to concomitant medication start) – (date of Study Day 1). If a participant has not had a negative assessment prior to the concomitant medication start date, they will be censored at 0 days.
 
All other participants will be censored with time to recrudescence censored at their last parasite assessment on or before Study Day 14, with time to recrudescence = (date of final parasite assessment) – (date of Study Day 1).

Number of Relapses

A participant is considered to have had at least one relapse if they:
 
demonstrated initial clearance of P. vivax parasitemia (defined as two negative asexual P.

Number of Relapses

vivax parasite counts, with at least 6 hours between the counts, and no positive counts in the interval)
 
subsequently had a positive asexual P. vivax parasite count at any assessment up to and including their Day 180 visit.
 
A participant is considered to have had a subsequent relapse if they:
 
demonstrated clearance of P. vivax parasitemia following their previous relapse (defined as a negative asexual P. vivax parasite count)
 
subsequently had a positive asexual P. vivax parasite count at any assessment up to and including their Day 180 visit.

Clearance time
Parasite (PCT)

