
Defined as: time needed to clear asexual parasite from the blood i.e. parasite numbers falling below the limit of detection in the thick blood smear and remaining undetectable ≥ 6 hours later.
 
If a participant has a non-zero asexual P. vivax parasite count at baseline, and prior to Study Day 8 has two negative counts with at least 6 hours between the counts and no positive parasite counts within this time period, parasite clearance time will be defined as the time elapsed between the first dose of study medication (including DHA-PQP) and the first of these negative counts (measured in hours).
 
Participants with a negative parasite count at baseline will be censored with a parasite clearance time of 0 hours. All other participants will be censored at the time of the last non-missing assessment prior to Study Day 8.

Gametocyte (GCT)

Defined as: time from first dose until the first slide that was gametocyte negative and remained so at the next slide reading.
 
Any participant with negative P. vivax gametocytes at baseline will be censored with a time to gametocyte clearance of 0 days.
 
For all other participants, gametocyte clearance will be considered to have been achieved once a negative gametocyte value has been seen, unless the next gametocyte count is positive. Time to clearance will then be defined as (time to first negative value) – (time of first dose of study medication including DHA-PQP).
 
Subjects who fail to reach this endpoint will be censored at the visit of their final gametocyte assessment.

Fever (FCT)

Defined as: time from first dose of treatment to the time when body temperature falls to normal and remains normal for at least 48 hours up to the Day 7 visit.
 
Any participant who does not have a temperature in excess of 37.4°C at any point prior to the first dose of study medication (including DHA-PQP) on Study Day 1 will be censored with a fever clearance time of 0 hours. Participants will also be censored at time 0 if the method of temperature measurement is not consistent throughout Study Days 1 to 7 (i.e., method is not consistently oral, tympanic, or axillary).
 
Fever clearance is considered to have been achieved once an initial temperature of >37.4°C is reduced to a value $\leq 37.4^\circ\text{C}$, in the absence of value >37.4°C in the following 48 hours

Clearance time

up to the Day 7 visit.

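### Parasite clearance time cannot count a man whose first lasting negative smear is Day 7: he is censored at about 144 h on a negative smear

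*SAP*

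**What the plan says.** SAP 11.6.3 (Clearance time, Parasite) makes clearance an event for a man with a positive baseline who "prior to Study Day 8 has two negative counts with at least 6 hours between the counts and no positive parasite counts" in between. The event time runs in hours from the first dose, DHA-PQP included, to the first of the two negatives. Apart from men with a negative baseline, who are censored at 0 hours, the rule is: "All other participants will be censored at the time of the last non-missing assessment prior to Study Day 8". It does not ask whether that assessment was positive or negative.

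On the smear schedule, Protocol 7.4 has slides taken "twice a day, 6-12 hours apart for the first 3 days, or until 2 consecutive negative thick blood smears are obtained". It continues: "Microscope blood slides will be prepared at subsequent visits on Days 7, 14, 21, 28, 60, 90, 120, 150 and 180". The Time and Events table marks smears on Days 1, 2, 3, 7 and 14 of the treatment period. SAP shell EFF_T1 goes from the second Day 3 assessment straight to Day 7.

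For the primary endpoint, SAP 11.6.3 defines initial clearance as two negative counts "with at least 6 hours between the counts, and no positive counts in the interval", with no Day 8 limit.

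SAP Appendix 1, footnote 2, reports three men who "were incorrectly concluded to have negative smears which were in-fact positive, and hence missed a subsequent parasitology assessment during days 1-3". They stay in the per-protocol population. Nothing is said about their clearance time.

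SAP 7.2.5.1 analyses the endpoint with Kaplan-Meier estimates and a Cox hazard ratio, and plans no sensitivity analysis. If proportional hazards fails, it substitutes logistic regression on event versus no event.

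**The concern.** The confirmation deadline and the smear schedule do not fit together. A first negative on Day 7 needs a second negative before Day 8, and no smear is scheduled to supply it. The man is recorded as not cleared on the strength of a negative smear, and the Day 14 result that would settle the matter is ignored. The primary analysis uses that same Day 14 result to call him cleared.

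Almost every man is expected to clear, so a few misclassified men account for most of the visible non-clearance in Table 2.17 and Figure 2.6. The logistic fallback, read naturally, would take them as non-events. A further problem arises if a man's last positive smear was early and later Day 1-3 smears were missed. He may have cleared well before Day 7, yet the rule keeps him at risk until about 144 h, past the times at which other men clear.

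**Working it through.** **Timing.** SAP 11.6.1 places Study Day 180 exactly 179 days after Study Day 1, so Day n is n − 1 days later. Day 7 is 6 × 24 = 144 h and Day 14 is 13 × 24 = 312 h. Clock times will vary around these.

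**Applying the rules to smear histories** (illustrative hours after first dose; positive baseline in every case):

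| History | Clearance time as written | Primary-endpoint clearance |
|---|---|---|
| A. Negative 24 h and 32 h | Event at 24 h | Cleared |
| B. Positive through 56 h; Day 7 and Day 14 negative | Censored at 144 h | Cleared |
| C. Negative 24 h, positive 32 h, smears stop; Day 7 and Day 14 negative | Censored at 144 h | Cleared |
| D. Positive 24 h, negative 32 h, smears stop; Day 7 negative | Event at 32 h | Cleared |
| E. Positive through 48 h, negative 56 h; Day 7 negative | Event at 56 h | Cleared |
| F. As E, but Day 7 missed; Day 14 negative | Censored at 56 h | Cleared |
| G. Positive on Day 7 | Censored at 144 h, correctly | Not cleared by then |

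The rule fails in B, C and F. In D and E the Day 7 smear already confirms an earlier negative.

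**Event count and tail.** With three men like B in an arm of 50, the rule gives 50 − 3 = 47 events and a final Kaplan-Meier value of 3/50 = 0.06. If Day 14 may confirm, there are 50 events and the tail is 0.

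**Hazard ratio.** The documents give no clearance-time distribution, so one has to be assumed. All runs use 50 per arm, no true difference, and all affected men in one arm.

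- *Positive through Day 3 (B).* With first-negative times spread over 8 to 56 h, the hazard ratio was 0.91, 0.85, 0.80 and 0.71 for 1, 2, 3 and 5 men. It was the same whether they were censored at 144 h, counted as events at 144 h, or censored at 56 h. The shift comes from placing late clearers in one arm. With Weibull times (shape 2, median 24 h) and three men, it was about 0.79 as written and 0.82 under either alternative.
- *Early last positive, then missed smears (C).* With the same Weibull assumption and three men, it was about 0.79 as written and about 0.95 if censored at the last positive. Moving the assumed median between 18 and 36 h left both figures essentially unchanged. For one man who truly cleared at about 32 h (8 to 56 h distribution), it was 0.91 as written and 0.99 with his true time.
- *Spread over arms.* It stays near 1.

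Under 1:1:1 allocation, the chance that all three footnote men share some arm is about 3 × (1/3)³ = 1/9.

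**The case against.** The strongest reply is that the endpoint is confirmed clearance, timed at the first negative smear. For a man positive through Day 3 that time is 144 h even when Day 14 confirms it, so censoring there agrees with his own event time. This stands. A reader might infer that every lone Day 7 negative gives falsely long follow-up and a biased hazard ratio; for history B the runs show little or no such effect.

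The affected group may also be empty. Protocol 4.1 and Time and Events note c can be read as continuing twice-daily smears until two consecutive negatives, in which case the problem needs missed smears. Protocol 7.4, the visit table and EFF_T1 point to stopping after Day 3, so the ambiguity remains. Nor does footnote 2 show that three men are affected: it does not say which smear was misread, and a man like D is already handled correctly. The supportable count is 0 to 3, plus any man still positive at his last Day 3 smear.

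A reader might also infer that the differing clearance deadlines in SAP 11.6.3 distort the recrudescence results. They serve different endpoints, and shell TTE6 shows only recrudescence versus censored. A man negative on Days 7 and 14 is censored there in any case.

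**Conclusion.** The point holds in a limited form. As written, the rule cannot count a man whose first lasting negative is Day 7, and it discards a Day 14 result that the primary analysis accepts.

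For men positive through Day 3, the cost is an understated number cleared, a false Kaplan-Meier tail and misclassification in the logistic fallback; the hazard ratio is little affected. For a man with an early last positive followed by missed smears, there is also a real hazard-ratio bias. The shift to about 0.8 is a worst case: it assumes that all three footnote men are of this type and in one arm, and it rests on an assumed clearance distribution.

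The documents do not support reading this as a threat to the primary result, which uses its own clearance rule without the Day 8 limit. It is a correctable flaw in the derivation of a named secondary endpoint.

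**What to change.** In SAP 11.6.3 (Parasite clearance time):

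1. Where the first negative is seen before Study Day 8, let the next smear at least 6 hours later confirm it, including Day 14, provided no positive falls between. Keep the event time at the first negative.
2. Censor men still unconfirmed at their last positive smear rather than their last non-missing smear.
3. Where smears were missed between the last positive and the first negative, add a sensitivity analysis that censors at the last positive smear. Step 1 alone would time a man like C at 144 h. The alternative is one interval-censored model for all men; applying it only to selected men would not fit the planned Kaplan-Meier and Cox analysis.

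The recrudescence derivation need not change. The cost is a few sentences of SAP text and a small amount of programming, more if the interval-censored model is chosen. No new data are needed.

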- i) Blood sample to be collected for CYP2D6 genotyping and stored for possible G6PD genotyping. Sample for G6PD genotyping may be analyzed in the event of an SAE due to hemoglobin decline where a repeat G6PD phenotype assay would not define G6PD status (e.g. transfusion given or high reticulocyte count).
- j) Dipstick urinalysis to be only done at screening.
- k) PK samples must be taken 6-12 hours and 24-48 hours post blinded dose of tafenoquine.
- l) Methemoglobin will be measured daily up to Day 14, alternate days up to Day 28 and on Day 60.
- m) Hematology/clinical chemistry to be done at relapse/withdrawal (up to Day 120 only).
- n) PK will be done as close to the time of relapse as possible (up to Day 60 only).
- o) Vital signs on Day 3 will be done immediately after ECGs (ie before the last of the three daily doses of DHA-PQP and 4 (-1 to +2) hours after the last dose of DHA-PQP).
- p) The D195 assessment is only required for subjects who do not relapse prior to D180 and receive open label primaquine (0.5mg/kg daily for 14 days) at the end of the study. Subjects who have relapsed prior to Day 180 will complete the study at D180.

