#### a) Procedures to be performed prior to DHA-POP administration

- Demographic data will be collected to include details of year of birth, gender, race and ethnicity.
- Medical history will be collected including cardiovascular history and associated risk factors.
- A physical examination will be conducted including:
  - Cardiovascular examination
  - Abdominal examination including an assessment of splenomegaly
  - Respiratory examination
- Vital signs will be assessed including height, weight, systolic and diastolic blood pressure, temperature (oral, axillary or tympanic), heart rate and respiratory rate. The same methodology should be used for measurement of temperature for all subjects.
- Investigators will assess *P. vivax* malaria symptoms at baseline. The incidence and severity (defined as absent, mild, moderate, severe, or unknown) of the following symptoms will be recorded: chills and rigours, headache, dizziness, abdominal pain, anorexia, nausea, vomiting, diarrhea, pruritis or itching, and coughing. The date of onset of symptoms will also be recorded. The investigator or designee can also assess and record any other *P. vivax* malaria symptoms.
- Blood smears for parasitological assessment will be collected and examined for asexual parasite count and gametocyte blood count (see Section 7.4 and the SRM for further details).
- Current and prior medications will be reviewed including any anti-malarial medication that has been used.

- A blood sample will be collected for *Plasmodium* genotyping analysis. An additional blood sample will be collected for future exploratory plasmodium whole genome sequencing (if parasite counts allow) (See Section 7.4 and Section 7.7).
- G6PD status will be assessed using the Fluorescent Spot Test (FST) or other suitable Point of Care Test (see SRM) to determine the subject's eligibility. An additional Point of Care Test (in development) may also be performed but the results of this test would not be used for eligibility. The quantitative spectrophotometric G6PD analysis will also be performed but results will not be available at the time of randomization. If results are discordant, the subject will be reviewed and appropriate G6PD testing will be repeated.
- Hematology and clinical chemistry assessments will be performed (refer to Section 7.5.5).

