Participants who do not demonstrate this endpoint prior to final assessment of Study Day 3 will be censored at that time point.

Participants with missing data in Study Days 1-3 will be censored at the last available temperature assessment, if they do not meet the definition of fever clearance before the Day 7 visit.

CPD2D6 Activity and Metabolizer Phenotype

Eijkman Institute will provide CYP2D6 *alleles which will be used to derive metabolizer class (Poor metabolizer (PM), Intermediate metabolizer (IM), Extensive metabolizer (EM), Ultra metabolizer (UM)).

Each of the two CYP2D6 *alleles, comprising the genotype, will be assigned a value relative to its activity compared to the *1 reference allele:

Value of 0 for null activity alleles: *3, *4, *5, *6, *7, *8, *11, *15

Value of 0.5 for reduced activity alleles: *9, *10, *14, *17, *29, *41

Value of 1 for fully functional alleles: *1, *2, *35

For all *alleles that are not captured above, the activity score will be determined prior to unblinding the data.

Alleles denoting gene duplications, represented by 'xN', will receive double the non-duplicated value. For example, *1xN will receive a value of 2 whereas *1 receives a value of 1.

The CYP2D6 Activity Score (AS) [Gaedigk, 2008] is then calculated as the sum of activity values from the two alleles comprising the genotype. For example, a participant with 2 null alleles will have an AS of 0; one null and one reduced activity allele will have a score of 0.5; or one null allele and one fully functional allele will have an AS of 1.

The CYP2D6 phenotype will be classified based on the AS and follows the Dutch Pharmacogenomics Working Group [DPWG] classification scheme, where:

Poor metabolizer if AS = 0

Intermediate metabolizer if AS = 0.5 or 1

Extensive metabolizer if AS = 1.5 or 2

Ultra metabolizer if AS \geq 2.5

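### The fever-clearance rule censors at time 0 for any thermometer change on Days 1 to 7, so a reading outside the 48-hour window can remove a clearance already met

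*SAP*

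**What the plan says.** SAP 11.6.3, under fever clearance time, sets a consistency condition on the thermometer: "Participants will also be censored at time 0 if the method of temperature measurement is not consistent throughout Study Days 1 to 7". It explains this as the case where the "method is not consistently oral, tympanic, or axillary". The condition covers the whole week and does not ask whether clearance was reached before the method changed.

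The same entry describes the event in two ways. The headline definition needs a temperature that falls to normal and "remains normal for at least 48 hours up to the Day 7 visit". The operational sentence needs a first value at or below 37.4°C, "in the absence of value >37.4°C in the following 48 hours".

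Two further rules limit the timing. "Participants who do not demonstrate this endpoint prior to final assessment of Study Day 3 will be censored at that time point". Men with missing Day 1 to 3 temperatures are censored at their last available reading, but only "if they do not meet the definition of fever clearance before the Day 7 visit".

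On measurement, protocol 7.2 instructs: "The same methodology should be used for measurement of temperature for all subjects". The protocol 7.1 schedule has temperature before dosing on Day 1, on Day 2, on Day 3 and on Day 7. Note o to that table makes Day 3 two readings: "Vital signs on Day 3 will be done immediately after ECGs", that is, before and about 4 hours after the last DHA-PQP dose.

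**The concern.** A consistency rule should protect the readings that establish the event. This one reaches past them. A man can be febrile at baseline, read normal on Day 2 and stay normal through the next 48 hours, all by one method, and still be moved to time 0 by a later reading that plays no part in the operational criterion. Whether he counts in the fever analysis is then settled by something recorded after his event.

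Fever clearance is one of the secondary blood-stage endpoints, and only men febrile at baseline can contribute, so its information is already limited. SAP 7.2.5.1 plans no sensitivity analysis for it. The loss would also be hard to see: the footnote to listing EFF_L3 (SAP Appendix 12) explains a censored time of zero solely as absence of baseline fever, which would mislabel febrile men removed for a method change. The primary relapse analysis is not touched.

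**Working it through.** The documents give no sample size, power or event count for fever clearance, so there is no figure of the plan's own to reproduce.

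**Step 1: can Day 7 fall inside the 48-hour window?** Study days are calendar dates (SAP 11.6.1) and the Day 7 analysis window is Day 7 only (SAP 11.3.1). The last date for a first normal value under the Day 3 deadline is Day 3. Days 4, 5 and 6 lie wholly between, so the gap to Day 7 is more than 3 × 24 = 72 hours. It is always outside the window.

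**Step 2: apply the rule to one man.** These are invented test values: 38.6°C before the first dose, 36.9°C at 24 h, 36.8°C at 47.5 h and 36.7°C at 52 h, all axillary. His 48-hour window runs from 24 h to 72 h. The Day 7 reading, 36.6°C at 144 h, comes 144 − 24 = 120 h after the first normal value.

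| Day 7 reading | SAP as written | Check limited to baseline through first normal + 48 h |
|---|---|---|
| Axillary | Event at 24 h | Event at 24 h |
| Missing | Event at 24 h | Event at 24 h |
| Tympanic | Censored at 0 h | Event at 24 h |

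A normal reading by another device does what no reading at all would not do. A man censored at time 0 is in no risk set at any event time, so this amounts to exclusion.

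**Step 3: compare with the SAP's handling elsewhere.**
- Missing Day 1 to 3 temperatures: censored at the last available reading, and only if clearance was not met (SAP 11.6.3).
- Antimalarial use without relapse, where there was initial clearance: censored at the last negative smear before the drug, with time 0 only if there is none (SAP 11.6.3, six-month endpoint).
- Relapse and a censoring reason in the same man: the relapse stands (same place).
- SAP 11.7.2.2 says mITT participants are not left out of any statistical analysis.

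The thermometer rule departs from each of these.

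**Step 4: size, under assumptions.** No switching rate is documented. Let q be the chance that a post-baseline reading uses another method, independently for each reading. Take a man first normal on Day 2. He has 4 scheduled post-baseline readings through Day 7, of which 3 (Day 2 and two on Day 3) fall within the span needed for clearance.

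| q | Any switch, 1 − (1 − q)^4 | Switch by late Day 3, 1 − (1 − q)^3 | Lost to Day 7 alone, q(1 − q)^3 |
|---|---|---|---|
| 0 | 0% | 0% | 0 points |
| 2% | 7.8% | 5.9% | 1.9 points |
| 5% | 18.5% | 14.3% | 4.3 points |
| 10% | 34.4% | 27.1% | 7.3 points |

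Only the last column measures this point. Men in the third column have mixed methods among the readings that matter.

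**Step 5: precision.** For two equal arms, SE(log HR) ≈ √(4/E) with E events. If a share s of otherwise valid clearances is lost, the interval widens by a factor 1/√(1 − s), whatever E is. For s = 5%, 10% and 20% this is 1.026, 1.054 and 1.118. As an example, assume 50 of the 100 men in two arms are febrile and clear. Losing 20% leaves 40 events, and the SE rises from √(4/50) = 0.283 to √(4/40) = 0.316. Under the Step 4 model s equals q, because (1 − q)^4/(1 − q)^3 = 1 − q. The 20% case would need something more clustered, such as a change of device.

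**The case against.** The strongest reply is that Day 7 may be part of the confirmation. Any Day 2 and Day 3 readings are less than 48 hours apart, and nothing is scheduled on Days 4 to 6. If normality must be observed for 48 hours, Day 7 is the only scheduled reading that can show it, and a different method there breaks the chain. The headline definition leaves room for this. The operational sentence does not require it: it asks only that no febrile value be recorded in the 48 hours. The Day 3 deadline and the missing-data rule also treat clearance as achievable before Day 7. Even on the stricter view, a missing Day 7 reading would fail to confirm just as a mismatched one does, and the SAP does not say so. The ambiguity stands and should be resolved in the text.

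The rule also has a sound purpose. One cut-off of 37.4°C serves oral, axillary and tympanic readings, so declining to mix methods within a man is defensible. It is pre-specified and does not depend on arm. The protocol asks for one method for everyone, so switches may be rare or absent. All of this stands, and it limits the size of the point.

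Simply discarding readings by another method would be a poor remedy. A man at 37.0°C axillary on Day 2 and 38.6°C tympanic on Day 3 would then be declared clear at about 24 hours. This also stands, and the fix below allows for it.

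A reader might infer that men with persisting fever, who return for extra readings, are removed more often, so that clearance looks faster. The documents do not support this. Protocol 7.3 leaves procedures at unscheduled visits to clinical indication, and nothing says which thermometer is used there. Bias would need switching to be related to outcome or arm, and neither is shown.

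**Conclusion.** The point holds in a limited form. As written, the rule can remove a clearance that meets the operational definition on single-method readings, because of a later reading outside the 48-hour window. The consequence is lost events and exclusion by post-baseline data in one secondary endpoint. The size is unknown and is zero if nobody switches. Under assumed per-reading switch rates of 2% to 10%, the loss due to Day 7 alone is 1.9 to 7.3 percentage points of febrile men. An assumed loss of 5% to 20% of valid clearances widens the interval by 2.6% to 11.8%.

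The 7.8% to 34.4% figures should not be read as the damage done: they rest on invented rates and include men whose confirming readings are truly mixed. The conclusion also rests on the operational sentence, not the headline one, governing the derivation. It is a cheap improvement and not a threat to the trial's conclusions.

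**What to change.** In SAP 11.6.3:
- Apply the method check only from the febrile baseline reading through the 48 hours after the first normal reading.
- If the method changes within that span, or before clearance, censor at the last same-method reading before the change. Use time 0 only if there is none.
- Do not disregard a value above 37.4°C by another method within the 48 hours. Treat it as not confirming clearance.
- State whether the Day 7 reading is part of confirmation, and if so, what a missing one means.

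In the displays, report the number of method-censored men by arm and extend the EFF_L3 footnote to name a method change as a second reason for a censored time of zero.

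The cost is a few SAP sentences, one footnote, one count and slightly more programming. The method field is already needed for the existing rule, so no new data are required.
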